The next step in evaluating the advisability of geriatric obesity treatment is to determine whether such benefits achieved during a period of relatively intense obesity treatment are retained over time, a so called “legacy effect”. A legacy effect has happened when the benefits from a treatment or intervention are shown to persist when the intervention is no longer being administered (put both references here instead of after next sentence). “Metabolic memory,” a related term, has been used to describe the long-term impact of intensive diabetes treatment (9, 10). The potential that a short-term treatment could yield long-term benefits could be especially promising for obese older adults, who often face a number of obesity-related comorbidities and may not be able to sustain the extra burden of an ongoing weight control regimen. Unfortunately, only two studies, to our knowledge, have explored the legacy effect of obesity reduction in older adults (11, 12), and only the study by Waters et al. (12) reported physical function outcomes. These investigators conducted an 18-month follow-up assessment in 16 frail, obese older subjects who had participated in a one year, single-armed weight loss plus exercise trial; they confirmed maintenance of benefits to body weight, physical function, insulin sensitivity, and other metabolic markers. Chmelo et al. (13), conducted an 18-month follow-up to a 5-month trial of resistance training (RT) versus resistance training plus caloric restriction (RT +CR), assessing body weight and composition as well as thigh composition but not physical function. They reported loss of thigh muscle mass in both groups and found weight regain and increased total fat mass in the RT +CR group.

While obesity interventions have been shown to provide dramatic functional benefits, the sustainability of these results over time and the net long-term impact on function is unknown.

Very recently (Figures 1 and 2 below; manuscript in preparation), we have shown a “legacy effect” of obesity treatment in this population; finding that the functional benefits of an intense period of intervention persist for a year or more, even if there has been weight regain. Given this exciting finding, we hypothesize that a practical, sustainable

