telehealth intervention can be developed and implemented to magnify and extend these important legacy benefits. In the proposed research, we will 1) utilize experiences from the target population and experts in the field to develop a program of novel telehealth technologies to maintain and extend the legacy benefits of obesity treatment, and 2) evaluate the feasibility of this treatment in a pilot study of obese, functionally frail older adults.

2 Study Objectives

AIM 1a: In a series of semi-structured interviews with obese, functionally frail older adults who recently completed an intensive obesity intervention, we will collect key qualitative information on determinants (facilitators and barriers) of success in maintaining the functional benefits of obesity treatment over time. In ≥24 past weight loss intervention study completers (within 6 to 24months), we will conduct semi-structured interviews with 1) past participants who have maintained their weight loss and functional improvements, to identify personal beliefs, behaviors, and environmental factors that facilitated their success, and 2) past participants who have regained their weight, to identify personal beliefs, behaviors, and environmental factors leading to their treatment relapse.

AIM 1b: Utilizing results of Aim 1a, along with elements of our previously established evidence-based obesity intervention, we will develop a tele-nutrition and tele-exercise program intended to maintain and extend the benefits of a recent obesity intervention. Utilizing the information obtained from the semi-structured interviews and in consultation with experts in the area of telehealth, we will create a novel program of tele-nutrition and tele-exercise guided by the Social Cognitive Theory.³ The goal will be to maintain and extend the functional and quality of life benefits achieved in an intensive obesity intervention for older adults.

AIM 2: We will conduct a 3-month program of tele-nutrition and tele-exercise in 10 obese, functionally frail older adults who have successfully completed an obesity intervention (lost 5% of their body weight and increased SPPB by 1 point) and determine its feasibility, acceptability, and fidelity. Specifically, we will evaluate the feasibility (recruitment/retention)

[figure not shown]

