4.3 Early Withdrawal of Subjects

4.3.1 When and How to Withdraw Subjects

Participants may be withdrawn from the study if they are disruptive during the group discussions or cannot be contacted by the study staff after initial contact.

5 Study Procedures

AIM 1a: Collect key qualitative data on determinants (facilitators and barriers) of success in maintaining the functional benefits of obesity treatment over time.

Interview Participants: The [name] Nutrition Lab at Duke University currently have two ongoing weight loss interventions in obese, older adults. We will contact our past participants, who previously agreed to be contacted for future research study, and successfully completed a lifestyle intervention (lost at least 3% body weight and increased short physical performance battery (SPPB) score by 1 point or 6-minute walk test (6MWT) by 50 meters) within the last 6 to 18 months. Participants who pass the telephone screen are willing to participate will be consented (Table 1), weighed, and complete the SPPB and 6MWT to determine their current functional status. Participants will then be separated into one of two groups, **Maintainers** or **Non-maintainers**, based on their current functional status (Table 2; n=12 to 15 per group or until thematic saturation is reached in each group). Next, semi-structured interviews will be conducted to identify personal beliefs, behaviors, and environmental factors that facilitated their success or treatment relapse.

Table 1. Inclusion/Exclusion Criteria Aim 1a

Inclusion Criteria	Exclusion Criteria

 Participated in a weight loss intervention in the last 6 to 18 months and lost \geq 3% body weight and improved SPPB score by \geq 1 point or 6MWT by \geq 50 meters (Perera et al. J Am Geriatr Soc. 2006;54(5):743-9) Age \geq 60 Able to speak and understand spoken and written English. 	
 Presence of unstable or symptomatic life-threatening illness Neurological conditions causing functional impairment, including Parkinson's disease, multiple sclerosis, and permanent disability due to stroke Inability to complete physical function assessment Unwilling to have their individual interview audio recorded History of cognitive impairment

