Setting: Screening will be conducted by telephone. Consents will be sent electronically and a consent presentation will be conducted virtually using Duke Zoom. Consented participants will come to the Duke Center for Living Stedman Center and will complete SPPB and 6-minute walk to determine their group assignment based on functional outcomes (Table 2). Next, using telephone or Duke Zoom, participants will undergo a guided semi-structured interview (sample interview guide for both groups below).

Table 2. Aim 1a Participants

Groups	Criteria	Social Cognitive Theory
Maintainers	Physical function improvements were maintained	Personal, environmental, and behavioral facilitators
Non-maintainers	Physical function improvements were regressed	Personal, environmental, and behavioral barriers

Note to IRB: This is an interview guide for semi-structured qualitative interviews of participants as laid out in the study protocol. The interviewer will use this guide to organize the interview. Because it is a guide, exact questions may vary during the course of the interview or order may vary somewhat depending on answers given by participants. However, the guide provides a general structure and order for questions and ensures that all domains are covered in the interview as appropriate, based on the answers of the participant being interviewed. The interviewer will adhere to the guide, but will also follow the conversation, which may stray from the guide as he/she feels is appropriate.

Sample semi-structured interview guide for the Maintainers

1. Personal

1. Do you see yourself differently than you did before or during the study?
2. How does it feel to have maintained your weight loss/function status?
3. What is your definition of success, as it relates to your weight or health?
4. What's one thing that is contributing to your success of maintaining weight loss/continuing to eat healthy?
5. When you think of other goals you have achieved, what about you do you believe helped you to achieve them?
 1. Can you describe a personal attribute that helped you maintain your weight loss?
6. How do you feel about your body? About your health?

2. Behavioral

1. What activities reinforce your motivation to eat healthy meals and/or move your body?
2. What behaviors have helped you be successful?
3. How have your behaviors changed since completing the study?
4. Describe the process of changing your behavior long term.

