5. What were your expectations of losing weight? Were those expectations met?
6. Has COVID-19 impacted your ability to maintain your nutrition and physical activity habits? If so, how? If not, why?

3. Environmental

1. What outside yourself helps you to maintain your weight loss or achieve other goals?
2. What outside yourself is crucial to your success?
3. Describe the support outside of yourself that helps you maintain activities/choices that support your health?
4. Did you experience an event, idea, or person that reinforced your commitment to maintaining weight loss?
5. How does your culture/community affect your eating/exercise habits?
6. How does your family/friends influence your behavior?
7. How did your social support network (friends, family, colleagues) react to your weight loss?

Sample semi-structured interview guide for the Non-maintainers

Personal

1. What thoughts do you have about your weight journey since you completed the study?
2. How do you feel about your body? About your health? About your current weight?
3. What about your personality or experiences affects your health/nutrition choices?
4. What has worked for you in the past regarding _____ (exercise, weight loss, diet)?
5. Has there been a time when you were successful and how did that make you feel?
6. If you could change one thing today regarding your health, what would that be?
7. Is there anything about your health or your weight that concerns you?
8. Describe your approach to other goals you have
 - a) Why do you think you were able to achieve those goals?
 - b) Why do you think you were not able to achieve those goals?

Behavioral

1. Have you maintained any habits that you acquired during the study? Why or why not?
2. Do you cook and if so, do you enjoy it?

a) If so, how would you describe your cooking skills?

Beginner/intermediate/advanced/expert

3. What about diet is important to you?
 - a) What health habits are important to you?
4. What concerns, if any, do you have about your current level of physical activity?
5. What concerns, if any, do you have about your current eating habits?
6. When you tried _____ (dieting, Eggspsdite) in the past, what got in the way?
 - a) If it was a person - what would it take to get them on board with your habit changes?
 - b) If it was finances/access to food - have you ever used community resources to help improve your access to food?
7. Describe your personal process of trying to adopt long lasting behavior change.

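### The Aim 1a question and groups concern physical function, but the sample interview guides seldom raise function and lean toward weight and eating

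*Combined protocol and SAP*

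**What the plan says.** Section 5 states the Aim 1a task as finding "determinants (facilitators and barriers) of success in maintaining the functional benefits of obesity treatment over time". After consent, participants are weighed and complete the SPPB and 6-minute walk. They are then placed in a group "based on their current functional status". Table 2 gives the criteria: for Maintainers, "Physical function improvements were maintained"; for Non-maintainers, "Physical function improvements were regressed". Weight is measured but does not assign the group.

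Section 2 describes the groups differently. The first is "past participants who have maintained their weight loss and functional improvements"; the second is people who regained weight, with function not mentioned.

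Section 1.1 gives the investigators' own finding that the "functional benefits of an intense period of intervention persist for a year or more, even if there has been weight regain".

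Section 5 then prints a sample guide for each group. A sub-item under Personal 5 in the Maintainer guide asks "Can you describe a personal attribute that helped you maintain your weight loss". The Non-maintainer guide opens with "What thoughts do you have about your weight journey since you completed the study". Section 6 organises the interview data by the guide questions, applies a priori and then emergent codes, compares factors between groups, and reports on what influences keeping the functional benefits.

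**The concern.** The guide is the instrument that turns the Aim 1a question into data. If the question and the group label concern function while most topical prompts concern weight and eating, the answers may describe determinants of weight and then be compared across groups defined by function.

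The Maintainer wording adds a second problem. On the investigators' own evidence, a person can keep function and regain weight. Table 2 makes that person a Maintainer, who may then be asked what helped achieve something that did not happen.

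At stake are the clarity of the between-group contrast and the material available for the tele-exercise half of Aim 1b. Table 4 later scores tele-exercise adherence by whether functional status was maintained, so function matters in Aim 2 as well.

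**Working it through.** The plan gives no figure to reproduce here. The check is a content count of the two guides in Section 5, followed by a comparison of the two group descriptions.

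**Denominators.** Maintainer guide: Personal 6 + 1 sub-item, Behavioral 6, Environmental 7, so 6 + 1 + 6 + 7 = 20. Non-maintainer guide, numbered items with lettered parts folded in: 8 + 9 + 5 = 22. Total 20 + 22 = 42.

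**Counts by keyword** (an item can fall under more than one):

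| Item mentions | Maintainer (20) | Non-maintainer (22) | Both (42) |
|---|---|---|---|
| Function | 1 | 0 | 1 |
| Weight | 8 | 5 | 13 |
| Eating, diet, cooking, food | 4 | 10 | 14 |
| Weight or eating | 11 | 14 | 25 |
| Exercise or activity | 3 | 6 | 9 |
| None of these (open) | 9 | 7 | 16 |

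The rows reconcile: 25 items on weight or eating, 1 on activity alone, and 16 open make 42.

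**The function item.** Maintainer Personal 2 joins weight loss and function status with a slash and asks how it feels to have kept them. It does not ask what brought that about.

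**The activity items.** Of the 9, 8 pair exercise or activity with eating, diet or weight. The other one, Non-maintainer Behavioral 4, asks about concerns over current activity level. None refers to walking, balance or strength, which the SPPB and 6-minute walk measure.

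**Items that assume weight was kept.** Five Maintainer items use maintained-weight-loss wording. Two offer a way out: Personal 2 (function status) and Environmental 1 (other goals). That leaves 5 − 2 = 3 with no function or other-goal alternative: Personal 4, the Personal 5 sub-item and Environmental 4. They are not equally strong. Personal 4 also allows healthy eating, Environmental 4 asks about commitment, and the Personal 5 sub-item is the plainest case.

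**Group descriptions side by side.**

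| Function | Weight loss | Table 2 | Section 2 |
|---|---|---|---|
| Kept | Kept | Maintainer | First group |
| Kept | Regained | Maintainer | Second group |
| Lost | Kept | Non-maintainer | Neither |
| Lost | Regained | Non-maintainer | Second group |

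The second row is where the three items misfit, and it is the pattern that Section 1.1 describes. Under Section 2 those people would not receive the Maintainer guide.

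**Reach.** The thin coverage of function applies to every interview: 2 × 12 = 24 to 2 × 15 = 30, matching the minimum in Section 2 and the maximum in the Study Summary. The misfit of the three items applies only to Maintainers who regained weight. The documents give no proportion, so at the planned group size this is anywhere from 0 to 15 people.

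**The case against.** A reader might infer that the guides ask only about weight and eating, and so cannot supply what Aim 1b needs. The documents do not support that, for five reasons.

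- Nine items touch exercise or activity and 16 are open, including what behaviours helped and which study habits were kept and why. Diet and exercise are plausible determinants of function, so an item can be informative without naming it.
- The guides are labelled samples, wording and order may vary, and Section 6 speaks of guide questions still to be developed with specialist input.
- Section 6 adds emergent codes within each category, so coding is not confined to the guide's own terms.
- Aim 1b builds tele-nutrition as well as tele-exercise, the Study Summary describes a weight-maintenance intervention, and Table 4 scores tele-nutrition adherence on weight. Weight and eating content is needed. Aim 1b also draws on the existing intervention and on expert input.
- Under the Section 2 description, the Maintainer weight items assume nothing false.

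These points limit the concern without removing it. Section 5 also says the interviewer will keep to the guide and relies on it to cover all domains, so the central outcome should not be left to improvisation. Section 2 conflicts with the operative rule in Section 5, and its own Aim 1a question is still about functional benefits. The counts involve some judgement, and the lettered Non-maintainer parts are folded in. Counting those 8 parts separately would give 0 of 30 for function, since none names it.

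**Conclusion.** The concern holds in a limited form. Followed as written, the sample guides under-probe the outcome that Aim 1a and Table 2 are about: function is named in 1 of 42 items and no item asks directly why it was kept or lost. Three Maintainer items also presume kept weight loss, which Table 2 does not require. This may weaken the comparison between groups and the input to tele-exercise.

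Two stronger inferences are not supported. The documents do not show that the interviews will fail to yield usable determinants. Nor do they show that the Maintainer group will contain people who regained weight, only that it may.

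The conclusion assumes that Table 2 is the operative grouping rule and that interviewers stay close to the printed guides. If Section 2 governs, the presumption problem falls away, but the lack of direct function questions remains. The point merits correction before interviews start; it does not threaten the aim.

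**What to change.** Before the first interview:

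1. Add the same direct question to both guides, for example: what has helped you, or made it harder, to keep the walking, balance and strength you gained in the study? Keep the existing weight, eating and exercise items.
2. Make the weight-maintenance items conditional on the weight taken at the Aim 1a visit, so that a Maintainer who regained weight is asked about that instead. The measurement is already planned.
3. Add physical function to the codebook as an a priori structural code, separate from weight.
4. Reconcile the Section 2 group description with Table 2, so that one definition governs both the grouping and the guide wording.

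The cost is edits to the protocol text, guides and codebook, and slightly longer interviews. No extra participants, visits or measurements are needed.

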A Novel Telehealth Intervention using Nutrition and Exercise to Extend Intervention Benefits:
Enhancing Physical Function in the Long-term for Obese Older Adults

Pro 00105630

Version 1.0

4/24/2020

NCT04490356

Regulatory Sponsor: [name] [name]
Duke University
Department of Orthopaedic Surgery
[name]
[name]
[name]
[name]

Funding Sponsor: National Institutes of Health (NIH)

Study Summary

Title	A Novel Telehealth Intervention using Nutrition and Exercise to Extend Intervention Benefits: Enhancing Physical Function in the Long-term for Obese Older Adults
Short Title	Enhancing Physical Function in the Long-term for Obese Older Adults
Protocol Number	Pro00105630
Phase	N/A
Methodology	Qualitative individual interviews and/or focus groups will be conducted in-person or via the phone with: obese older adults who previously (within the last 20 months) participated in a weight loss intervention Single-arm pilot intervention investigating the feasibility, fidelity, and acceptability of a tele-nutrition and tele-exercise 3 month weight maintenance intervention
Study Duration	1 year
Study Center(s)	Single-center
Objectives	This study seeks to develop and test the feasibility, acceptability, and fidelity of a tele-nutrition and tele-physical activity weight-maintenance intervention tailored towards obese older adults who recently lost weight.
Number of Subjects	Up to 60 (Aim 1: up to 30; Aim 2: up to 20)
Diagnosis and Main Inclusion Criteria	Past participants of weight loss intervention for obese, older adults
Study Product, Dose, Route, Regimen	N/A
Duration of administration	N/A
Reference therapy	N/A
Statistical Methodology	We plan to use applied thematic analysis for the semi-structured interviews and focus groups. Descriptive statistics, proportions for feasibility, adherence and retention will be calculated, and student's t-test will be conducted to compare weight change over time in the pilot study.

1 Introduction

This document is a protocol for a human research study. This study is to be conducted according to US and international standards of Good Clinical Practice (FDA Title 21 part 312 and International Conference on Harmonization guidelines), applicable government regulations and Institutional research policies and procedures.

1.1 *Background*

[figure not shown]

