of an intervention designed to extend legacy benefits, its acceptability (as assessed by attrition and participant satisfaction), and its fidelity (as assessed by adherence). Additionally, we will access physical function (SPPB) at 0 and 3 months.

3 Study Design

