3.2 Primary Study Endpoints

Individual interview group feedback (transcripts) to identify personal beliefs, behaviors, and environmental factors that facilitated their success or treatment relapse.

Determine the feasibility, acceptability, fidelity of a tele-nutrition and tele-physical intervention.

4 Subject Selection and Withdrawal

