SPPB (6, 64, 66)	0, 6, 12 weeks	Balance (side-by-side, semi-tandem, tandem), gait speed (4-meter timed walk), strength (chair stands).
6-minute walk test (aerobic endurance)	0, 6, 12 weeks	As many walking laps as possible in six minutes between cones placed 40 meters apart
Questionnaires		
Quality of Life; Mood; Depression; Stress; Sleep; Life Satisfaction	0, 6, 12 weeks	SF-36; CES-D; Perceived stress; Pittsburgh sleep
Acceptability		
Participant Satisfaction Questionnaire	12 weeks	Participants will be asked to rate their satisfaction using a five point Likert scale (very dissatisfied; dissatisfied; neutral; satisfied; very satisfied) on a) satisfaction with the delivery of the tele-nutrition intervention, b) satisfaction with the delivery of the tele-exercise intervention c) satisfaction with their ability to maintain their physical function d) satisfaction with their ability to maintain their weight loss e) satisfaction with interactions with the registered dietitian.
Feedback Session	12 weeks	Using an interview guide we will examine aspects of the program in-depth from participants' perspectives.
Attrition Rate	12 weeks	Attrition Rate (%) = (Number of dropouts ÷ number of total participants) x 100
Feasibility		
Feasibility	12 weeks	Proportion of participants recruited will be calculated as the number of patients deemed potentially eligible and contacted for enrollment divided by the total number of patients enrolled.
Fidelity		
Adherence to tele-nutrition intervention	12 weeks	Proportion adherent to the tele-nutrition intervention will be computed by dividing the number of participants who maintained their weight by the total number of participants
Adherence to the tele-exercise intervention	12 weeks	Proportion adherent to the tele-exercise intervention will be computed by dividing the number of participants who maintained their functional status by the total number of participants
Retention	12 weeks	Proportion retention will be computed by dividing the number of retained subjects at the end of the intervention by the total number of participants

Risk/Benefit Assessment

The risk to human subjects for participation in this study is minimal compared to the potential health benefits they will receive from participating in the interventions and receiving detailed nutrition and exercise information.

Physical Risks:

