Aim1a: A qualitative analytical approach is well suited to exploring concepts related to a complex process (long-term adherence to weight loss and physical activity). We plan to use applied thematic analysis, organizing the data in response to the a priori questions contained in the semi-structured interviews and interview guides. Interview guide questions will be developed utilizing input from the Interventionist and socio-behavioral researchers. We will use applied thematic analysis to analyze the data. Audio recordings will be transcribed verbatim following a transcription protocol. Two analysts will use NVivo 12 software to develop and apply structural (a priori) codes to segment participants' narratives into conceptual categories (e.g., all text describing a similar concept, such as psychosocial factors). Next, analysts will identify and apply content-driven (emergent) codes to the text for each of the conceptual categories (e.g., potential themes related to psychosocial factors). Inter-coder reliability assessments will be conducted on approximately 25% of transcripts during both structural and content coding. Discrepancies in coding will be resolved through analyst discussions; transcripts will be re-coded and the codebook revised accordingly. Once coding is complete, we will examine code frequencies across transcripts to identify salient factors for each interview group, followed by comparing and contrasting factors between groups. To conclude analyses, analytical memos and reports will be written, describing the factors influencing success in maintaining the functional benefits of obesity treatment over time, together with illustrative quotes.

Aim 2. Feasibility: Proportion of participants recruited will be calculated as the number of participants deemed potentially eligible and contacted for enrollment divided by the total number of participants enrolled. Proportion retention will be computed by dividing the number

of retained participants at the end of the intervention by the total number randomized into the study. Fidelity: Proportion adherent to the tele-nutrition diet and tele-exercise intervention. Acceptability: Levels of attrition will be calculated and satisfaction will be assessed with survey items on a Likert-scale and focus group.

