We will calculate these rates of retention, adherence, and attrition and their respective confidence intervals overall. While non-powerful, in a series of sensitivity tests, we will assess if adherence overall was impacted by demographic/socioeconomic variables.

We will employ a simplified applied thematic analysis for the feedback session recording and transcript following a similar approach to 1a above, less the NVivo interface and group comparison given the single group. Assessment of our measures used with screening/recruitment, adherence/retention, attrition/participant satisfaction, physical function, and self-efficacy will inform our feedback session interview guide where we will examine aspects of the program in-depth from participants' perspectives. This will allow us to examine individual level success through our objective intervention documentation in tandem with rich data from participants during the feedback session.

For physical function outcome measures a repeated measures analysis of variance will be employed to determine differences between timepoints, followed by pairwise comparison of each time point to the baseline time point.

7 Safety and Adverse Events

Oversight and Reporting: [name] will be responsible for the operation of this research study according to the study's protocol and IRB policies. Any serious adverse event, study-related or not study related will be reported via email to the Duke University IRB within 24 hours of learning about the event. Within 5 business days following the initial report, a Notification of a Problem or Event Requiring Prompt Reporting Form will be sent to the Duke IRB. This study is not an intervention and thus will not have a safety monitoring board, however the investigator will submit the number of adverse events, complaints, withdrawals, and protocol violations to the Duke University IRB. In addition, the PIs will review quarterly adverse event reports and make adjustments to the protocol if needed.

We expect adverse events to be limited to loss of protected health information. The study team has outlined procedures for data management to protect against loss of data (detailed below). Breaches in data security will be reported within 24 hours of detection, and a plan for management of the breach and modification of data security procedures will be developed within 3 business days, if applicable.

8 Data Handling and Record Keeping

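### Both Table 4 adherence proportions count participants who kept their weight or function, so the fidelity endpoint reports clinical outcomes under an adherence label

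*Combined protocol and SAP*

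**What the plan says.** Section 3.2 gives the Aim 2 primary endpoint as "Determine the feasibility, acceptability, fidelity of a tele-nutrition and tele-physical intervention". Section 2, Aim 2, says how the third of these is measured: "its fidelity (as assessed by adherence".

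The only formulas are in Table 4 (Section 5), under Fidelity. Adherence to tele-nutrition is obtained by "dividing the number of participants who maintained their weight by the total number of participants". Adherence to tele-exercise is obtained by "dividing the number of participants who maintained their functional status by the total number of participants". Both are taken at 12 weeks. A third row in the same block is retention.

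The Aim 2 text of Section 6 adds only "Fidelity: Proportion adherent to the tele-nutrition diet and tele-exercise intervention", with no definition of adherent.

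The plan also analyses the same two quantities as outcomes. The Study Summary says a "t-test will be conducted to compare weight change over time in the pilot study". Section 6 says "For physical function outcome measures a repeated measures analysis of variance will be employed".

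**The concern.** Adherence describes what participants did with the programme. Weight and function describe what happened to them. The Table 4 rows use the second to stand for the first, so both kinds of misclassification are possible. A person who joins no class and keeps no journal, but whose weight and function hold, is scored adherent. A person who does everything asked and still declines is scored non-adherent.

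Section 6 says the pilot is to supply preliminary data for a larger trial. For that purpose the team needs to know whether people took up the programme. The two proportions alone cannot separate poor uptake from a programme that does not work, or good uptake from benefit carried over from the earlier weight-loss intervention.

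**Working it through.** **1. Trace the endpoint to its formula.** Section 3.2 names fidelity, Section 2 measures fidelity by adherence, and Table 4 scores adherence as weight or function maintained. Section 6 repeats the term without a rule. Table 4 therefore governs.

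**2. Check whether the plan treats adherence and outcome as distinct.** It does. Section 2 lists fidelity and then adds SPPB as a further assessment. Section 6 names adherence with retention, and physical function as a separate item, among the measures that inform the feedback session. Weight and function each have their own test. The Table 4 rows therefore conflict with the plan's own structure.

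**3. Check what else could carry adherence.** Table 4 lists a daily food journal that bears an adherence label and is assessed by a dietitian, and a weekly step count. Neither enters a fidelity formula. No session-attendance measure is listed. Retention records who was still in the study at the end, not whether they followed either component, and Sections 2 and 6 place it under feasibility.

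**4. Is maintenance without participation plausible?** For function, yes. Section 1.1 reports that functional gains lasted a year or more after the earlier intervention, even with weight regain. Aim 2 enrols within 3 months of that intervention and ends at 12 weeks, so the final assessment falls at very roughly 3 + 3 = 6 months. For weight, Section 1.1 is mixed: one cited follow-up found maintenance and another found regain. The text gives no rate for either.

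**5. Illustrate the consequence.** Let *a* be true uptake, and let *m1* and *m0* be the chances of maintaining with and without following the programme, among those assessed at week 12. Then

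reported adherence = a × m1 + (1 − a) × m0.

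This equals *a* at every level only if m1 = 1 and m0 = 0. Otherwise it equals *a* at the single point a* = m0 / (1 − m1 + m0), reads too high below that point and too low above it. All m1 and m0 values here are assumptions; none is in the documents. Worked cell: 0.5 × 0.9 + 0.5 × 0.7 = 0.80.

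| Assumed m1 / m0 | a = 0% | a = 50% | a = 100% | a* |
|---|---|---|---|---|
| 0.9 / 0.7 | 70% (+70) | 80% (+30) | 90% (−10) | 0.7/0.8 = 87.5% |
| 0.7 / 0.7 | 70% (+70) | 70% (+20) | 70% (−30) | 0.7/1.0 = 70% |
| 0.4 / 0.2 | 20% (+20) | 30% (−20) | 40% (−60) | 0.2/0.8 = 25% |

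Brackets show the error in percentage points. The sign depends on values that the documents do not supply.

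**6. Check the denominator.** The plan's enrolment figure reproduces: 10 / (1 − 0.30) = 14.3, rounded up to 15. Table 4 divides by all participants. If 15 enrol, 10 complete and dropouts count as not maintained, neither proportion can exceed 10/15 = 67%. The 70%, 80% and 90% of the first row would then become 7/15 = 47%, 8/15 = 53% and 9/15 = 60%. Table 4 does not say how dropouts count in the numerator. It also gives no reference value or tolerance for maintained, and does not say whether functional status means SPPB, 6-minute walk or both.

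**The case against.** The strongest case for leaving the plan alone has four parts.

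*Fidelity is not scored wholly by outcome, and behavioural data are collected.* A reader might infer that the plan has no participation measure. That goes too far, given the retention row, the journal and the step count. What stands is that none of these is turned into adherence to a programme component.

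*Maintenance is a fair proxy, and the bias is hypothetical.* A reader might infer that the plan will overstate adherence. The documents do not support that, because every m1 and m0 above is assumed. The +70-point cells also need people who follow none of the programme yet attend the final assessment. Nor does lasting benefit over the pre-intervention level mean that function holds at its Aim 2 starting level. The mislabelling stands without any of these numbers.

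*The plan does not predict maintenance without the programme.* A reader might infer a prediction from Aim 1a, which recruits Maintainers defined by "Physical function improvements were maintained". But Aim 1a seeks the same number of Non-maintainers, 12 to 15 per group. These are sampling quotas, at 6 to 18 months by the Table 1 criteria, and say nothing about frequency.

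*It is a small pilot with an openly stated formula.* This is true. There is no success threshold or hypothesis test on the fidelity proportion. Effects on the check of adherence against demographic variables are minor, since the plan concedes that check lacks power. A 10-point subgroup difference is half a person in a group of five (0.10 × 5 = 0.5). This lowers the severity but does not remove the point: the fault is one of definition, so a larger sample would not cure it.

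**Conclusion.** The point holds. Followed exactly, the plan reports two clinical outcomes as adherence for one component of the Aim 2 primary endpoint. This rests on comparing the plan's own definitions and needs no assumed value.

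Its numerical size is unknown. The documents support neither a claim that adherence will be inflated nor a claim that it will be deflated. The legacy finding only makes maintenance of function without participation plausible.

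This is a should-fix matter. The study is a single-arm pilot with about 10 completers and sets no fidelity threshold, so no pass or fail decision turns on the figure. It still deserves correction before Aim 2 enrolment, because attendance not logged at the time may not be recoverable.

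**What to change.** In Table 4 and Section 6:

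- Relabel the two existing proportions *weight maintained* and *function maintained*. Report them as preliminary outcomes against the Aim 2 baseline. Before Aim 2 enrolment, state the functional measure used, the tolerance for each proportion, and how dropouts count in the numerator.
- Report adherence from participation, with all enrolled as the denominator and each component shown separately, not combined: percentage of offered exercise sessions attended, percentage of offered nutrition sessions attended, and percentage of expected food-journal entries completed. State the number of expected entries, because the journal is called daily while its Table 4 row lists only weeks 0, 6 and 12.
- If the step tracker is part of the final programme, its wear or use may be reported descriptively.
- Fix the component list and a cut for each component after Aim 1b, when the content is known, and before Aim 2 enrolment.

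The cost is small: two relabelled rows, the added adherence definitions, a revised Section 6 sentence, and staff time to log attendance and journal completion. No extra visits are needed, and the existing proportions are kept under accurate names.
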